keeping bladder pressures low (2) preservation of urinary continence and (3) optimizing quality of life. Clinicians use anticholinergic medications or onabotulinum toxin A to relax or paralyze the bladder musculature and minimize bladder spasticity. By decreasing bladder spasticity, a low-pressure system is established, which protects renal function and allows patients to store urine without significant incontinence. Patients must also employ some form of assisted bladder emptying, such as an indwelling catheter or clean intermittent catheterization (CIC) to drain the bladder. These strategies can significantly reduce urinary complications and related hospitalizations, especially in those patients who tolerate the medications and have the dexterity to perform CIC independently. However, there is a significant inconvenience, potential dependence on others, and often continued leakage that leads to patient noncompliance and discontinuation of CIC^{4,9,10}. Patients who fail these less invasive treatments may require surgical bladder augmentation or urinary diversion in order to preserve renal function¹¹. Bladder augmentation and urinary diversion surgery are both effective, but are associated with significant surgical morbidity and a 1-3% risk of death from complications. Furthermore patients often require additional surgical care during their lifetime to maintain their complex reconstructed urinary system¹².

Complications associated with NGB dysfunction and management. In the past, renal failure and urinary sepsis were the major causes of death in SCI patients after recovery from initial injury¹³. However, advances in urologic care, specifically the introduction of CIC in the 1970's revolutionized the care of SCI patients^{14,15}. In contemporary studies, the leading causes of death in SCI patients are now pneumonia and influenza rather than renal failure¹⁶⁻¹⁸. As a result of longer life expectancy, the chronic complications of NGB management are more prevalent and cause significant morbidity¹⁹. Five primary risks of NGB dysfunction and associated management are described below, namely: urinary tract infection, urinary calculi, bladder cancer, renal dysfunction and pressure ulcers.

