Pressure ulcers (PrU): The relationship between NGB dysfunction, bladder management method and PrU is less direct. Bladder and bowel incontinence have been suggested as risk factors for PrU in some studies but not in others³⁴⁻³⁶. A proposed mechanism of PrU resulting from incontinence is wetness of the skin resulting in softening of the protective nature of the dermis and accelerating the impact of pressure on the skin, an effect which is more pronounced when the wetness is due to urine³⁷. PrU prevalence is 39% over three years in Veterans with SCI³⁸, and grade 3-4 PrU are well established risk factors for mortality in SCI¹⁸.

Previous study of NGB treatment has focused on how to best control pressures in the bladder, as well as minimize complications once chronic NGB dysfunction has developed after the acute phase of SCI has past. Very few studies have attempted to prevent or ameliorate the adverse sequelae of NGB dysfunction in the acute phase of SCI. Since chronic NGB cannot be reversed, prevention of the development of some of the worst aspects of NGB such as high pressures and spasticity may be the next best strategy.

Sacral neuromodulation (SNM) is an available technology, which may mitigate the effects of SCI on the bladder. Over the past 20 years SNM has become an established treatment for refractory urinary urge incontinence, urinary frequency/urgency syndrome, non-obstructive idiopathic urinary retention and chronic fecal incontinence³⁹⁻⁴². Since first FDA approval in 1997 for refractory urinary urge incontinence, more than 40,000 people have been implanted with SNM devices⁴³. The surgical procedure is minimally invasive and has very few risks. A quadripolar electrode is placed with fluoroscopic guidance adjacent to the S3 nerve routes within the sacral foramen. An internal pulse generator (IPG), much like a cardiac pacemaker, is connected to the electrode and the S3 nerve is stimulated with varying patterns and intensity. The mechanism of action of neuromodulation in humans is not well understood, but it is thought to be through the same afferent sensory nerve fibers (A-delta and C), which are implicated in the development of NGB.

Sacral neuromodulation has a very well established track record in the treatment of patients with non-neurogenic urinary and fecal dysfunction. In the US, the

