Despite the success of the above studies in selected populations of patients with chronic NGB, once changes in the neurological control of the bladder have occurred following SCI they are mostly irreversible. In chronic NGB, treatments must be directed at the local muscle level in order to control the high bladder pressures, incontinence and other symptoms. Consequently, the majority of research into the effects of spinal cord injury on the urinary bladder has focused on patients with well-established chronic neurogenic bladder physiology.

Interventions during the acute phase of SCI aimed at preventing the development of, or reducing the symptoms of NGB, remain an understudied area of research.

Purpose and Objectives

AIM 1: To determine the effect of sacral neuromodulation on urodynamic parameters following acute spinal cord injury. The following outcomes will be evaluated by urodynamic assessment at one year post-SCI: (1) maximum cystometric capacity, (2) bladder compliance, (3) presence of detrusor overactivity, and (4) volume and pressure for first detrusor contraction.

AIM 2: To assess the impact of sacral neuromodulation on patient-reported quality of life after acute spinal cord injury. Patient-reported QoL will be assessed using the SCI-QOL bladder question bank and bladder/voiding diaries (Appendix B). Mean SCI-QOL score, daily number of catheterizations, average catheterization volume, and episodes of incontinence per day will be compared between groups at one year post-SCI.

AIM 3: To examine the impact of sacral neuromodulation on quantifiable clinical outcomes. Patients will be followed longitudinally during the study period and assessed for the following: (1) need for anti-cholinergic medications and/or onabotulinum toxin A treatment, (2) number of symptomatic UTIs per year, (3) complications attributable to the device, (4) need for revision of device or leads due to lead migration or failure, (5) development of hydronephrosis.

Study Population

Age of Participants: 18+

Sample Size:

At Utah: 20
All Centers: 60

Inclusion Criteria:

Inclusion Criteria
Age > 18 years
Ability to implant device less than 12 weeks post-SCI
Presence of acute SCI at or above T12
ASIA Scale A or B
Expectation to perform CIC personally or have caretaker perform CIC

Exclusion Criteria:

Exclusion Criteria

Inability to perform CIC

Pre-existing SCI

Pre-existing progressive neurological disorder

Autonomic dysreflexia

Prior sacral back surgery

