Posterior pelvic fracture with distortion of the sacroiliac joint

Prior urethral sphincter or bladder dysfunction

Chronic urinary tract infections prior to SCI

Pregnancy at the time of enrollment

Presence of coagulation disorder or need for anticoagulation that they cannot be stopped temporarily for procedure

Any significant co-morbidity or illness that would preclude their participation or increase the risk to them having a surgical procedure

Active untreated infection

Traumatic injury to the genitourinary system

Prior pelvic radiation, bladder cancer or other surgical procedure to the bladder that would effect baseline bladder physiology

Design

Prospective Clinical Research

Randomized

Phase I Clinical Trial

Study Procedures

Recruitment/Participant Identification Process:

PI and Research coordinators/Assistants will review charts for study eligibility. Then patients will be consented by a member of the study team.

We have also created flyers to be left in clinics with information about the study. The flyers will contain the coordinators contact information and inclusion/exclusion details about the study.

We will also recruit with the assistance via a Facebook advertisement. The Facebook ad will route to the NBRG.org site, Neurogenic Bladder Research Group, which is a site maintained by the study PI [name]. All site PI's are part of the Neurogenic Bladder Research Group. The Facebook ad will route to a page that contains 2 educational videos about the study, as well as the inclusion and exclusion information and a form to complete if someone is interested in participating in the study. Once the potential participant enters their

information and clicks on "Submit" button, the completed form information will be emailed directly to [contact], [name], who is the research coordinator at the University of Utah. [name] will be responsible to responding to all inquiries about the study via the Facebook advertisement.

We have had success with previous studies involving participants with a spinal cord injury with advertising through Facebook. The advertisement will allow us to reach a larger population of possible participants and their friends and family.

Informed Consent:

Description of location(s) where consent will be obtained:

Patients will be identified and consented in physical medicine and Rehab or neurosurgery or Urology clinics.

Description of the consent process(es), including the timing of consent:

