Once screened for inclusion and exclusion criteria (see above), patients will be approached and asked if they would like to participate in a randomized, non-blinded study within 12 weeks of the acute spinal cord injury event. Participants screened online through the Facebook advertisement will still require to be seen by the the site PI in clinic prior to consent to the study. They will then be given study material and informational video and allowed sufficient time to make an informed decision regarding participation. In the event that the participant is unable to read or sign the consent form because the participant is illiterate, visually impaired, or physically unable to sign, we will use a witness to confirm the consent process and sign/date the consent form. Not only will this help us achieve enrollment goals, but it will ensure patient safety and prevent discrimination.

Procedures:

PI and Research coordinators/Asistants will review charts for study eligibility. Future participants will have a choice to view an information video about the study. Then patients will be consented by a member of the study team.

Pregnant women will be excluded from participation. Women who are at risk of pregnancy will be asked to have a pregnancy test before taking part to exclude the possibility of pregnancy. Women of childbearing potential must use an effective contraceptive during the course of this study. Acceptable methods of birth control include abstinence, oral contraceptives, the contraceptive patch, the contraceptive ring and condoms.

60 patients will be enrolled and randomized (30 per arm) to either standard

neurogenic bladder management or standard management plus implantation of the Medtronic PrimeAdvanced Surescan 97702 Neurostimulator.

All patients will receive usual standard of care bladder management for neurogenic bladder. Specifically, standard treatment entails the following: (1) CIC at regular timed intervals if the patient is physically able to do so, if not able to physically perform self catheterization patients will have the option to have this performed by a caregiver (2) treatment with anticholinergic medicine or onabotulinum toxin A as indicated to increase bladder compliance, decrease urinary leakage, and lower bladder pressures to prevent renal damage, (3), undergo routine follow up in the urology and physical medicine and rehabilitation clinic, (4) upper tract imaging (typically consisting of a renal ultrasound) will be

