At each time point, a retrospective review since the prior time point will be performed in order to capture major events such as hospitalizations, additional surgery or death as well as additional subjective data. Those additional subjective data will include: (1) current usage of anti-cholinergic medications and/or onabotulinum toxin A treatment (2) number of culture proven symptomatic UTIs per year (3) complications attributable to the device, (4) need for revision of device or leads.

A renal ultrasound will be obtained at the end of 12 months to evaluate for the development of hydronephrosis. This will be compared with baseline CT or US imaging obtained during their initial trauma evaluation.

There will be a video available for participants to view for additional information.

Procedures performed for research purposes only:
Implantation of sacral neuromodulator and leads

Statistical Methods, Data Analysis and Interpretation

Sample size calculations for this study were based on a mean maximum cystometric capacity of 220.7 mL (SD=103.3), as reported by Sievert et al 60, and a feasibility of enrolling 30 patients per arm within the study period. After accounting for a 15% loss to follow-up we expect 25 evaluable patients per arm. To achieve 80% power at a 5% significance level with 25 patients per arm (N=50), we can detect an effect size of a 38% treatment effect (84 mL increase in capacity). This calculation was simulated for a two-tailed t-test incorporating one interim and one final look at the data using the O'Brien and Fleming (OBF) method and running 50000 simulations (using PASS v. 11.0.8 software). An interim analysis will be conducted at 50% enrollment (N=26 after loss to followup, 13 patients per arm) accrual, and the decision to stop early will be governed by an OBF significance level of 0.003. A 0.051 significance level will be used to evaluate the final analysis. The DSMB's decision to stop early will be guided both by interim results and clinical judgment, especially in the context of emerging, relevant literature.

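### Complications other than major events, UTIs and hydronephrosis are collected only if judged device-attributable, so they give no between-arm comparison

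*Combined protocol and SAP*

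**What the plan says.** Aim 3 (Purpose and Objectives) lists the clinical outcomes to be followed. From the third item on they read "3) complications attributable to the device, (4) need for revision of device or leads due to lead migration or failure, (5) development of hydronephrosis". The review at each time point (Study Procedures, Procedures) repeats the same restriction: "3) complications attributable to the device, (4) need for revision of device or leads". Neither place defines attribution or says who decides it.

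Other events carry no such condition. The same review is one in which "a retrospective review since the prior time point will be performed in order to capture major events such as hospitalizations, additional surgery or death", with no limit to one arm. It also records "2) number of culture proven symptomatic UTIs per year". A renal ultrasound at 12 months looks for hydronephrosis, and standard care for all patients includes annual serum creatinine.

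The Informed Consent section says that patients are asked to "participate in a randomized, non-blinded study within 12 weeks of the acute spinal cord injury event". The Procedures section keeps patients in their randomised arm, on an intention-to-treat basis, if motor responses cannot be elicited in theatre and no device is implanted. The statistical section deals only with maximum cystometric capacity and specifies no safety comparison.

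**The concern.** Randomisation allows total complications in the implant strategy to be set against total complications under standard care. An item that counts an event only once it has been blamed on the device cannot serve that purpose. Controls can contribute nothing to it, and the implant arm's count depends on the opinion of people who know the allocation.

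This matters more here than in a trial of an established use. The protocol calls the study Phase I, the stimulator is approved for a different stimulation site, and lead and generator are placed in one operation without the usual test period. A DSMB is to weigh interim results and clinical judgement, but the text plans no summary of harms by arm for it.

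**Working it through.** **The plan's own figure.** No safety figure is stated. The stated 80% power for capacity (84 mL, SD 103.3, 25 per arm) reproduces at 0.804 for a two-sided t-test and 0.808 in a simulation with the two planned looks. It is not in dispute, and the fix leaves the sample size unchanged.

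**Which events can be compared by arm, as the text stands**

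| Event | Attribution required? | Comparable by arm? |
|---|---|---|
| Hospitalization, additional surgery, death | No | Yes |
| Culture-proven symptomatic UTI | No | Yes |
| Hydronephrosis at 12 months | No | Yes |
| Device or lead revision | Device needed | No, by nature |
| Any other non-major complication | Yes, to the device | No |

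The last row is the gap. Within it, patients operated on but not implanted are a special case. They count in the implant arm but have no device, so a non-major event of theirs has no clear place on the form.

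**What the missing comparison could show, with pressure ulcers as the example.** The Background gives the only usable rate: "PrU prevalence is 39% over three years in Veterans with SCI".

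1. Assumption: read 39% as cumulative incidence at a constant rate. One-year risk = 1 − (1 − 0.39)^(1/3) = 0.152.
2. Expected patients with an ulcer per arm: 30 × 0.152 = 4.6 randomised, or 25 × 0.152 = 3.8 evaluable (the plan's 25 is 30 × 0.85 = 25.5, rounded down).
3. Power to detect a doubling (0.152 to 0.304) at 25 per arm, two-sided 5%, normal approximation. The mean proportion is 0.228.
   - SE under no difference = √(2 × 0.228 × 0.772 / 25) = 0.119.
   - SE under the alternative = √((0.152 × 0.848 + 0.304 × 0.696) / 25) = 0.117.
   - Power = Φ((0.152 − 1.96 × 0.119) / 0.117) = Φ(−0.69) ≈ 0.24.
4. Approximate 95% CI half-width for the difference when both arms are at 15.2%: 1.96 × √(2 × 0.152 × 0.848 / 25) = 0.20, or 20 percentage points.
5. Range: if 39% were instead the one-year risk (an upper bound), power for a doubling to 78% would be 0.82 and the half-width 27 points. The implant-arm rate detectable at 80% power is about 52% in the first case and 77% in the second.

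**The case against.** The strongest reply is that the plan already collects the harms that matter most, in both arms and without attribution. This stands. A reader might infer that harms of implantation never reach a between-arm comparison, but the documents do not support that. A pressure ulcer or an operative complication that led to admission, further surgery or death would be captured in either arm. The list of major events is also introduced by example, so it need not be exhaustive.

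Four further readings go too far:

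- **That operative or anaesthetic complications are excluded.** Implantation is named as the only research procedure, so an undefined attribution to the device can reasonably be read to cover it. The same uncertainty applies to an event during an interruption of anticoagulation, which the exclusion criteria contemplate ("need for anticoagulation that they cannot be stopped temporarily for procedure"). The fair criticism is that the term is undefined.
- **That the filter favours the device.** Only the implant arm can score on this item, and unblinded attribution can err either way. The direction is not established.
- **That pressure ulcers are certainly not collected.** They are absent from Aim 3 and the review list, but Table 1, which the protocol says lists all measured outcomes, is not in the available text.
- **That the Background commits the trial to measuring ulcers.** It names five risks ("urinary tract infection, urinary calculi, bladder cancer, renal dysfunction and pressure ulcers"), but these are risks of neurogenic bladder and its management. Stones and bladder cancer are likewise absent from Aim 3. The Background itself calls the ulcer link less direct.

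What remains after these concessions is a written collection rule, not a mere silence. Non-major complications other than UTI and hydronephrosis enter only through a judgement of cause.

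**Conclusion.** The point holds in a limited form. In the available text, complications below the level of a major event, apart from UTI and hydronephrosis, are collected only if judged attributable to the device. That item cannot give a contrast between arms, depends on undefined and unblinded attribution, and has no clear place for non-major events in patients operated on but not implanted.

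Correcting it would yield descriptive safety data that could exclude only large differences. The ulcer figures assume a constant rate and borrow a prevalence from Veterans with SCI, who may differ from patients enrolled within 12 weeks of injury. They illustrate scale and do not carry the point, which would stand without them. The conclusion would need revisiting if Table 1 shows general adverse-event collection in both arms.

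**What to change.** In Aim 3 item (3) and in the list for the review at each time point, replace the attribution-limited item with: all complications or adverse events since the prior time point, in both arms, using the same definitions, regardless of attribution. Record relatedness to the device or to the procedure as a separate field, and say who assigns it. In the statistical section, state that counts, rates and confidence intervals will be reported by randomised arm, with patients operated on but not implanted kept in the arm to which they were randomised.

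Naming pressure ulcers, with grade, on the form is an optional addition.

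The cost is protocol wording and more events to record in both arms at the existing 3-, 6-, 9- and 12-month reviews. No visit, test or change in sample size is needed. The documents give no basis for estimating the added staff time across the three centres.

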
NOTE: Implantation is usually accomplished via a two-step process involving a placement of the permanent quadripolar electrode alongside the S3 nerve root under local or general anesthesia. This permanent lead is controlled by a temporary external programming device for 7-14 days. If greater than 50% improvement in clinical symptoms over that test period, the IPG is implanted subcutaneously under during a second surgical procedure. Because the study hypothesis dictates early stimulation of the sacral nerve roots with a primary outcome evaluated one year post implant, the quadripolar electrical lead and IPG will be placed in the same procedure. This will avoid delay in stimulation of the sacral nerves during the critical window for preventing adverse neuroplastic changes. Patients will be mostly insensate due to their SCI or being under general anesthesia for the procedure. Therefore, to confirm intraoperative placement we will rely upon expected motor responses (anal bellows and toe flexion). If correct motor responses cannot be elicited intraoperatively than the patients will not undergo implantation and will be included in the randomized arm

but in an ‘intention-to-treat’ manner.

FDA approved programming parameters for the Interstim II system will be utilized in this study as follows. The device will provide continuous stimulation (i.e. always on) without discrete treatment periods. The PrimeAdvanced Surescan IPG is capable of generating a maximum voltage of 10.5 volts, 2 volts higher than the Interstim II system, however, it will be programmed to function within the normal Interstim II system parameters (maximum 8.5 volts). Additionally, it will be programmed to use the same stimulation pulsewidth (210 msec) and frequency (14Hz) as the Interstim II system. The area under the stimulation curve will be the same or less than intended by the Interstim II parameters.

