Each patient will be evaluated intraoperatively as is standard clinical practice to select stimulation parameters that result in typical, consistent physiological responses (e.g. anal bellows and first toe rotation). The default 14 Hz frequency will be maintained. The electrode with the lowest amplitude stimulation as a proxy for the most closely placed electrode to the S3 nerve. This electrode be trialed first. The stimulation amplitude will be set at 0.7V per protocol as was utilized in the one prior bilateral SNM study in acute SCI. Note: If the subject has S3 sensation (incomplete SCI), the amplitude will be set 0.1V lower than the level of sensation. In such sensate patients, each lead will be programmed individually and then both leads will be activated simultaneously to determine whether further amplitude reduction is needed. These parameters will be set during the initial programming session and will remain constant for the duration of the study. All study centers will utilize the same protocol.

Standardized demographic data based on the National Institutes of Neurological Disorders and Stroke (NINDS) Common Data Elements (CDEs) will be collected via patient interview and evaluation of the electronic medical record including mechanism of SCI and medical comorbidities. All measured outcomes are listed in Table 1 by Aim. At enrollment, all participants will complete the following: (1) standardized 3-day voiding diary to annotate the catheterization time, amount and time of fluid intake, and incontinence events, (2) 24 hour pad weight test, (3) 3-day bowel diary to quantify baseline bowel habits; (4) inventory of current medications; and (5) the SCI-QOL questionnaires (Appendix B). (6) 24 hour pad weight test averaged over 3 days. Repeat measurements will be obtained during clinic visits at 3, 6, 9, and 12 months after enrollment. (7) All participants will undergo baseline urodynamic testing at enrollment. For patients randomized to the intervention arm, urodynamic testing will be completed less than 2 weeks before implantation of the device. Urodynamic testing will be repeated at 3 months and then again at 12 months.

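### The only test named for maximum cystometric capacity is an unadjusted t-test, which is valid but gives no role to the baseline capacity planned for every participant

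*Combined protocol and SAP*

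**What the plan says.** The Statistical Methods, Data Analysis and Interpretation section gives the sizing basis: "Sample size calculations for this study were based on a mean maximum cystometric capacity of 220.7 mL (SD=103.3", a detectable difference of 84 mL, 80% power, a 5% level and 25 evaluable patients per arm. The test is named there and nowhere else: "This calculation was simulated for a two-tailed t-test incorporating one interim and one final look at the data". The interim look (13 per arm) uses a level of 0.003. For the last look, "A 0.051 significance level will be used to evaluate the final analysis". The supplied text contains no ANCOVA, change-score or mixed model.

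On measurement, the Procedures part of Study Procedures says: "All participants will undergo baseline urodynamic testing at enrollment". The next sentence adds: "For patients randomized to the intervention arm, urodynamic testing will be completed less than 2 weeks before implantation of the device". Urodynamics are repeated at 3 and 12 months.

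The time origin differs between sections. Aim 1 (Purpose and Objectives) lists capacity first of four urodynamic outcomes, assessed one year after injury. The implantation note refers to "a primary outcome evaluated one year post implant" without naming the outcome. The visit schedule reads: "Repeat measurements will be obtained during clinic visits at 3, 6, 9, and 12 months after enrollment". The implantation note also says that, where the expected motor responses cannot be elicited, "patients will not undergo implantation and will be included in the randomized arm" on an intention-to-treat basis.

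**The concern.** The natural reading is that the t-test used for sizing is also the analysis at both looks. If so, a pre-treatment measurement of the sizing variable, planned for everyone, is left out of the comparison.

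This matters because enrollment is set by feasibility at 30 per arm, and power sits at the 80% mark only for a 38% increase in capacity. A baseline measurement already in the plan is the cheapest available source of precision. Leaving the model unwritten also allows a choice between adjusted and unadjusted results after the data are seen, in a trial that is not blinded and has an interim look.

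**Working it through.** **Inputs from the Statistical Methods section.** SD 103.3 mL; difference 84 mL (0.38 × 220.7 = 83.9); 25 per arm (30 × 0.85 = 25.5, taken as 25); two-sided 5%; looks at 13 and 25 per arm at levels 0.003 and 0.051.

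**Assumed inputs.** The correlation r between enrollment and 12-month capacity (0 to 0.6) and the share of missing baselines (10% and 20%). The documents give neither.

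**1. Reproducing the plan's figure.** The standard error of the unadjusted difference is 103.3 × √(2/25) = 29.22 mL, so the noncentrality is 84/29.22 = 2.875. With 48 degrees of freedom the critical value is 2.011 and the noncentral-t power is 80.4%. Simulating two looks at 0.003 and 0.051 gives 80.4% to 81.1%. The stated 80% therefore corresponds to an unadjusted comparison on the full SD and takes no credit for baseline.

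**2. ANCOVA on baseline capacity.** The residual SD is 103.3 × √(1−r²). Estimating the slope costs one degree of freedom (47) and inflates the variance by 1 + 1/46. The standard error is 103.3 × √(1−r²) × √(2/25 × (1+1/46)). At r=0.5 it is 25.58 mL, so the noncentrality is 84/25.58 = 3.284 and the power is 89.6%.

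| Analysis | Power for 84 mL | Difference detectable at 80% power | Unadjusted n per arm with the same power |
|---|---|---|---|
| t-test | 80.4% | 83.5 mL | 25 |
| ANCOVA, r=0 | 79.6% | 84.5 mL | 24.5 |
| ANCOVA, r=0.2 | 81.1% | 82.8 mL | 25.4 |
| ANCOVA, r=0.3 | 83.2% | 80.6 mL | 26.8 |
| ANCOVA, r=0.5 | 89.6% | 73.2 mL | 32.3 |
| ANCOVA, r=0.6 | 93.6% | 67.6 mL | 37.7 |

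The two methods break even at r = 0.149.

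**3. Interim look** (13 per arm, level 0.003). Power is 14.0% for the t-test. For ANCOVA it is 13.0%, 13.8%, 14.9%, 19.9% and 25.1% at r = 0, 0.2, 0.3, 0.5 and 0.6.

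**4. Type I error over both looks at the plan's levels.** It is 0.051 to 0.053 by simulation for either test, so adjustment does not alter it.

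**5. Missing baselines.** Simulation with 100,000 runs per cell, baselines missing completely at random, single look at 5%:

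| Missing | Handling | r=0 | r=0.2 | r=0.3 | r=0.5 |
|---|---|---|---|---|---|
| 10% | Mean over both arms | 79.6% | 81.1% | 82.8% | 88.6% |
| 10% | Complete case | 74.8% | 76.5% | 78.6% | 85.8% |
| 20% | Mean over both arms | 79.5% | 80.7% | 82.2% | 87.4% |
| 20% | Complete case | 69.1% | 70.8% | 73.0% | 81.0% |

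Type I error with mean imputation is 0.049 to 0.051 throughout. Complete-case ANCOVA can fall well below the t-test's 80.4%, so the missing-baseline rule has to accompany the adjustment.

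**6. If baseline timing differed by arm.** Suppose the change in timing shifted mean baseline in one arm while the true effect is nil (25 per arm; shifts assumed). The bias in the adjusted difference is about r × shift. At r=0.5, a 25 mL shift gives a bias of about 12 mL and type I error of about 7.5%; a 50 mL shift gives 25 mL and about 15.5%. At r=0.3 the errors are about 6% and 8%. The unadjusted t-test is unaffected.

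**The case against.** The strongest reply is that nothing is broken. The t-test is unbiased under randomisation, the power claim reproduces, and sizing on an unadjusted test does not commit the trial to analysing that way. That is right, which is why the unadjusted analysis is described here as implied. But the model then still has to be written down.

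The second reply is that the gain may be negligible. The background section describes a bladder that is flaccid just after injury and changes over the following weeks, and implantation must occur within 12 weeks, so baseline falls in or near an unstable period. This stands: at r=0.2 the gain is 0.7 points and below about 0.15 there is a small loss. Nothing in the documents supports r of 0.5 or 0.6; those rows show the range only.

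The third reply is that adjustment could do harm if the sentence on testing before implantation describes a separate, arm-specific baseline. That risk is real (step 6). The simplest reading is a window on the same enrollment test, but it needs confirming before ANCOVA is adopted.

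Finally, the outcome's status may be settled elsewhere. The Procedures text points to a Table 1 of outcomes by Aim that is not in the supplied text, so the absence of a named primary outcome can be asserted only for the text available. The naming and time-origin items are side clarifications, and the case for adjustment does not depend on them.

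**Conclusion.** The point holds as a recommended change. It does not challenge the validity of the t-test or the sample size. With r unknown, prespecified ANCOVA risks at most 0.8 points of power if baseline is uninformative (80.4% − 79.6%). It gains 2.8 points at r=0.3 (83.2% − 80.4%), worth about 2 extra patients per arm, and 9.2 points at r=0.5 (89.6% − 80.4%), worth about 7. That balance rests on two conditions: participants without a baseline stay in the analysis, and the covariate is measured the same way in both arms. Confidence is medium, because r is an assumption and may be low.

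**What to change.** Before any comparative data are seen:

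1. Confirm that the covariate is the enrollment urodynamic test, done the same way in both arms, and that the two-week limit before implantation is a window on that same test. Adopt the adjustment only once this is settled.
2. Name maximum cystometric capacity at the 12-month visit as the outcome of the primary comparison, with one time origin that exists in both arms, such as months from enrollment. The control arm has no implant date.
3. Prespecify one model for both the interim and final looks: ANCOVA of 12-month capacity on randomised arm and enrollment capacity. Analyse by randomised group, including those randomised to the device but not implanted.
4. Replace a missing baseline with the mean over both arms, so that no one is dropped for lacking the covariate.
5. Report the unadjusted t-test as a sensitivity analysis.

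The cost is SAP wording and one clarifying sentence in Procedures. No new measurement is needed if the enrollment test is common to both arms, and the sample size stays at 30 per arm.
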